#### 8.1.2 Definition of Serious Adverse Events (SAE)

An AE or suspected adverse reaction is considered "serious" if, in the view of either the investigator or sponsor, it results in any of the following outcomes: death, a life-threatening adverse event, inpatient hospitalization or prolongation of existing hospitalization, a persistent or significant incapacity or substantial disruption of the ability to conduct normal life functions, or a congenital anomaly/birth defect.

The term "life-threatening" in the definition of "serious" refers to an event in which the patient was at risk of death at the time of the event; it does not refer to an event which hypothetically might have caused death if it were more severe.

Important medical events that may not result in death, be life-threatening, or require hospitalization may be considered serious when, based upon appropriate medical judgment, may jeopardize the patient or subject and may require medical or surgical intervention to prevent one of the outcomes listed in this definition. Examples of such medical events include allergic bronchospasm requiring intensive treatment in an emergency room or at home, blood dyscrasias or convulsions that do not result in inpatient hospitalization, or the development of drug dependency or drug abuse.

Events not considered being SAEs are hospitalizations for: a standard procedure for therapy administration, routine treatment or monitoring of the study indication, hospitalization or prolongation of hospitalization for technical/practical or social reasons in absence of an AE, a procedure which is planned. A prolongation of such a hospitalization for a complication remains a reportable SAE.

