## 8.2 Classification of an Adverse Event

### 8.2.1 Severity of Event

Intensity: all AEs will be graded according to the Common Terminology Criteria for AEs (CTCAE version 4.03) as follows (a semi-colon indicates ‘or’ within the description of the grade):

- Grade 1: Mild; asymptomatic or mild symptoms; clinical or diagnostic observations only; intervention not indicated.
- Grade 2: Moderate; minimal, local or non-invasive intervention indicated; limiting age-appropriate instrumental activities of daily living.
- Grade 3: Severe or medically significant but not immediately life-threatening; hospitalization or prolongation of hospitalization indicated; disabling; limiting self-care activities of daily living.
- Grade 4: Life-threatening consequences; urgent intervention indicated.
- Grade 5: Death related to AE.

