## **8.3 Time Period and Frequency for Event Assessment and Follow-Up**

The occurrence of an AE or SAE may come to the attention of study personnel during study visits and interviews of a study participant presenting for medical care, or upon review by a study monitor. All AEs including local and systemic reactions not meeting the criteria for SAEs will be captured on the eCRF. Information to be collected includes event description, time of onset, clinician's assessment of severity, relationship to study product (assessed only by those with the training and authority to make a diagnosis), and time of resolution/stabilization of the event. All AEs occurring while on study must be documented appropriately regardless of relationship. All AEs will be followed to adequate resolution.

Any medical condition that is present at the time that the participant signs the ICF will be considered as baseline condition and not reported as an AE. However, if the study participant's condition deteriorates in severity and frequency at any time during the study, it will be recorded as an AE.

Changes in the severity of an AE will be documented to allow an assessment of the duration of the event at each level of severity to be performed. AEs characterized as intermittent require documentation of onset and duration of each episode.

The Investigator will record all reportable events with start dates occurring any time after informed consent is obtained until 30 days (both AEs and SAEs) after the last day of study treatment. At each study visit, the investigator will inquire about the occurrence of AE/SAEs since the last visit. Events will be followed for outcome information until resolution or stabilization.

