#### **Adverse events**

AEs will be assessed according to the Common Terminology Criteria for AEs (CTCAE version 4.03).

The incidence of AEs will be tabulated by MedDRA System Organ Class and Preferred Term. The incidence of AEs will also be summarized by system organ class, preferred term and severity (based on CTCAE grades).

The same analysis will be repeated for SAEs regardless of drug relationship, for drug related SAEs, AEs with CTCAE grade 3 or 4 and for drug related AEs. AEs for which relationship to study drug is not specified will be considered treatment-related.

Deaths reportable as SAEs will be listed by patient and tabulated by type of AE.

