#### **Laboratory parameters**

Categorization of laboratory values will be assigned programmatically as per NCI Common Terminology Criteria for Adverse Events (CTCAE) version 4.03 or according to normal ranges for those parameters without available CTCAE grading. The calculation of CTCAE grades will be purely based on the observed laboratory values, clinical assessments will not be taken into account.

CTCAE Grade 0 will be assigned for all non-missing values not graded as 1 or higher. Grade 5 will not be used.

For laboratory tests where grades are not defined by CTCAE v4.03, results will be graded by the low/normal/high (low and high) classifications based on laboratory normal ranges.

The following by-treatment summaries will be generated separately for hematology, biochemistry and urinary laboratory tests:

- Worst post-baseline CTCAE grade (regardless of the baseline status). Each patient will be counted only once for the worst grade observed post-baseline.

- Shift tables using CTCAE grades to compare baseline to the worst on-treatment value.
- Shift tables using the low/normal/high/ (low and high) classification to compare baseline to the worst on-treatment value, for laboratory tests where CTCAE grades are not defined.

Listings of all laboratory data with values flagged to show the corresponding CTCAE grades and the classifications relative to the laboratory normal ranges will also be generated.

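### The dedicated severe-AE table is defined as CTCAE grade 3 or 4, so read literally it omits fatal (grade 5) events, and no grade 3-or-higher table is planned

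*Protocol*

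**What the plan says.** Protocol 10.4.4 (Adverse events) plans an incidence table of all AEs by system organ class (SOC) and preferred term (PT). It then adds a version by grade: "The incidence of AEs will also be summarized by system organ class, preferred term and severity (based on CTCAE grades". The same analysis is repeated for several subsets, one of which is "AEs with CTCAE grade 3 or 4 and for drug related AEs". SAP 6.6.1.5 uses the same words.

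The grading scale in protocol 8.2.1 runs from 1 to 5 and ends with "Grade 5: Death related to AE".

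Fatal events are also covered elsewhere:
- Protocol 8.1.2 makes an event serious if "it results in any of the following outcomes: death, a life-threatening adverse event" or another listed outcome follows. A fatal AE is therefore an SAE and enters the SAE tables.
- Protocol 10.4.4 states: "Deaths reportable as SAEs will be listed by patient and tabulated by type of AE".

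On recording, protocol 8.3 says: "Changes in the severity of an AE will be documented to allow an assessment of the duration of the event at each level of severity". On counting, the Laboratory parameters part of 10.4.4 counts each patient once at the worst post-baseline grade. The AE part has no matching rule.

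**The concern.** A table of severe adverse events is normally read as everything from grade 3 upwards. Here the wording stops at grade 4. A patient whose pneumonia or sepsis is fatal can be missing from the row for that term, while a patient who survives the same event is counted.

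This is foreseeable in the population under study. Protocol 2.1 lists pneumonia as very common and sepsis as common with daratumumab, and protocol 1.3 links moderate and severe renal impairment to a higher risk of early death. Safety is a secondary endpoint and the trial has one arm, so there is no control group with the same omission to compare against.

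The missing counting rule adds ambiguity. Two programmers following the SAP could produce different grade 3 or 4 rates from the same data.

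**Working it through.** The documents give no AE counts or expected rates, so there is no plan figure to reproduce. The check has a reading part and an arithmetic part.

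**Reading**

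1. Is grade 5 a valid AE grade in this trial? Yes, by protocol 8.2.1.
2. Does any text exclude grade 5 from AE tables on purpose? No. The sentence "Grade 5 will not be used" stands under Laboratory parameters and concerns grades assigned by program from laboratory values.
3. Does either document plan a grade 3-or-higher AE table? No. The SAP repeats the protocol wording without widening it.
4. Take a pneumonia recorded at grade 3 that later becomes grade 5. Counted at worst grade, it is outside the grade 3 or 4 table. Counted at each recorded grade, it is inside. Protocol 8.3 allows both records to exist ("Changes in the severity of an AE will be documented"), and nothing in 10.4.4 or SAP 6.6.1.5 chooses between them.

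**Arithmetic (illustration only)**

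Inputs:
- N = 38, the planned number of patients (protocol 10.5), taken as the size of the Safety Set.
- s = patients with a non-fatal grade 3 or 4 AE and no fatal AE (assumed).
- f = patients with a fatal AE (assumed).
- k = those among the f who also have a counted grade 3 or 4 record (assumed).

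Formulas:
- Rate in the table as worded: (s + k)/N
- Rate for grade 3 or higher: (s + f)/N
- Gap: (f − k)/N, which does not depend on s

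With s = 20:

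| f | k | As worded | Grade 3 or higher | Gap (points) |
|---|---|---|---|---|
| 1 | 0 | 20/38 = 52.6% | 21/38 = 55.3% | 2.6 |
| 3 | 0 | 20/38 = 52.6% | 23/38 = 60.5% | 7.9 |
| 5 | 0 | 20/38 = 52.6% | 25/38 = 65.8% | 13.2 |
| 3 | 3 | 23/38 = 60.5% | 23/38 = 60.5% | 0 |

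Each affected patient costs at most 1/38 = 2.6 points.

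For a single group of terms, assume 10 patients with grade 3-or-higher infection, or 10/38 = 26.3%. If 1 is fatal, the table as worded shows 9/38 = 23.7%. If 3 are fatal, it shows 7/38 = 18.4%. Both figures assume that no fatal case has another counted grade 3 or 4 infection record, which is the worst case.

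The patient-level and term-level results can differ. A patient with a fatal pneumonia and a separate grade 3 anaemia still counts once in the overall grade 3 or 4 rate, but the pneumonia row can lose that case.

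**The case against.** The strongest reply is that nothing is lost. The by-grade table has no upper limit, so grade 5 appears there by SOC and PT. If patients are counted at worst grade, its grade 3, 4 and 5 columns add up to the missing figure. Fatal AEs are also in the SAE tables and in the deaths listing and table. No test, stopping threshold or decision rule uses the grade 3 or 4 table; the safety review in protocol 10.4.7.1 is an overall evaluation with no numerical limit.

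Most of this stands. A reader might infer that fatal events vanish from the safety report, or that the drug will look safer as more severe events become fatal. The documents do not support either reading: the same deaths raise the grade 5 counts, the SAE counts and the death table.

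The other tables do not fully replace the missing one, however:
- The by-grade columns can be added only if each patient is counted once per term at the worst grade, and that rule is not written.
- The SAE tables measure seriousness, not severity. Protocol 8.4.3 has events of special interest, including infusion-related reactions, reported as SAEs even when considered non-serious, so lower-grade events may be included.
- Adding the death table to the grade 3 or 4 table is right only if no patient is in both, which the plan leaves open.

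**Conclusion.** The point holds for one table. As worded in both documents, the dedicated severe-AE table omits grade 5, and no grade 3-or-higher table is planned.

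The effect on the reported rate is conditional. It arises when events are counted at worst grade and, at patient level, only when the patient has no other counted grade 3 or 4 event. Under those conditions it is up to 2.6 points per affected patient at N = 38; otherwise it is 0 at patient level. The event counts behind any larger figure are assumptions, since the documents give none.

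A fall in the severe-event rate should therefore not be stated as certain. It depends on a counting rule that the plan has not set. The primary analysis, sample size and error rate are not affected. This is a minor reporting defect, worth correcting because any omission makes the table more favourable and the correction is nearly free.

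**What to change.** In protocol 10.4.4 and SAP 6.6.1.5:
1. Define the subset table as CTCAE grade 3 or higher (3, 4 and 5).
2. State that each patient is counted once per SOC and PT at the maximum grade reached, as is already done for laboratory values. Apply the same rule to the by-grade table so that the two agree.
3. Show grade 5 as its own column, so that fatal cases can be identified within the total.

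The cost is a change of phrase and one added sentence in each document. No new data are needed, because grades and changes in severity are already collected. The only downside is a severe-AE figure that may be slightly less favourable.

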#### **Laboratory parameters**

Categorization of laboratory values will be assigned programmatically as per NCI Common Terminology Criteria for Adverse Events (CTCAE) version 4.03 or according to normal ranges for those parameters without available CTCAE grading. The calculation of CTCAE grades will be purely based on the observed laboratory values, clinical assessments will not be taken into account.

CTCAE Grade 0 will be assigned for all non-missing values not graded as 1 or higher. Grade 5 will not be used.

For laboratory tests where grades are not defined by CTCAE v4.03, results will be graded by the low/normal/high (low and high) classifications based on laboratory normal ranges.

The following by-treatment summaries will be generated separately for hematology, biochemistry and urinary laboratory tests:

- Worst post-baseline CTCAE grade (regardless of the baseline status). Each patient will be counted only once for the worst grade observed post-baseline.

- Shift tables using CTCAE grades to compare baseline to the worst on-treatment value.
- Shift tables using the low/normal/high/ (low and high) classification to compare baseline to the worst on-treatment value, for laboratory tests where CTCAE grades are not defined.

Listings of all laboratory data with values flagged to show the corresponding CTCAE grades and the classifications relative to the laboratory normal ranges will also be generated.

### **Other safety data**

ECGs, vital signs and ECOG PS will be listed and summarized.

#### **ECG**

- Shift table baseline to worst on-treatment result
- Listing of ECG evaluations for all patients with at least one abnormality
- Change from baseline QTcF

#### **Vital signs**

- Table with descriptive statistics at baseline, one or several post-baseline time points and change from baseline to this/these post-baseline time points

#### **ECOG PS**

- Shift tables comparing the baseline PS with the worst post-baseline result

### **10.4.5 Baseline Descriptive Statistics**

All data about patient demographics and baseline characteristics will be summarized on the FAS, overall, by means of summary descriptive statistics.

A complete description of patient disposition will be provided, specifying the number of enrolled patients, number of patients at each visit, completed and discontinued patients, and the reason for the discontinuation.

The analysis populations will be described and the reasons for excluding the patient from any analysis set will be provided with the number of protocol violators per each criterion.

Medical history data will be presented by MedDRA System Organ Class and Preferred Term.

### **10.4.6 Treatments (study treatment, concomitant therapies)**

The Safety set will be used for the following analyses.

#### **Investigational treatment**

Duration of study treatment, cumulative dose, average daily dose, actual dose intensity and relative dose intensity of each of the components of study treatment will be summarized and for every 28-day cycle. The number of patients with dose changes/interruptions will be, along with the reasons for the dose change/interruptions.

### **Concomitant treatments**

Concomitant medications or procedures and significant non-drug therapies taken concurrently with the study treatment will be listed and summarized by WHO Anatomical Therapeutic Chemical (ATC) Class, Preferred Term. These summaries will include medications starting on or after the start of study treatment (defined as cycle 1 day 1) or medications starting prior to the start of study treatment and continuing after the start of study treatment. Any prior medication or significant non-drug therapy starting and ending prior to the start of study treatment will be listed.

For the analyses of transfusions, only transfusions received after start of study treatment and up to 30 days after last dose will be considered. The number of patients with transfusions and number of transfusions per patient will be analyzed.

### **10.4.7 Planned Interim Analyses**

No formal interim analysis for efficacy is planned. An interim analysis for safety will be performed as described below.

#### **10.4.7.1 Safety Review**

The Sponsor Scientific Committee will perform an overall evaluation of the safety data when 19 patients (50%) have received at least 1 dose of daratumumab. If a safety signal is identified and the Sponsor Scientific Committee determines that the safety profile of the study treatment is unfavorable, the recruitment of the rest of the subjects will be interrupted and the study may be stopped due to safety concerns. In the event of such a study termination all current subjects that are receiving daratumumab treatment may receive subsequent alternative treatment outside of the study as per the investigator's judgement and routine practice. More details on the Interim Safety Review will be provided in the Statistical Analysis Plan for this study.

#### **10.4.7.2 Efficacy Review**

No formal efficacy review is planned.

### **10.4.8 Additional Sub-group Analyses**

Additional sub-group analyses will be detailed in the Statistical Analysis Plan.

### **10.4.9 Multiple Comparison/Multiplicity**

Unless stated otherwise, one-sided alpha level 0.025 will be considered. No alpha level adjustment will be carried out for primary and secondary endpoints.

### **10.4.10 Exploratory Analyses**

Additional exploratory analyses will be detailed in the Statistical Analysis Plan.

## 10.5 Sample Size

The calculations were based on previous data for daratumumab in patients with relapse or refractory myeloma. The median PFS with daratumumab treatment in the SIRIUS study was 5.6 months in patients who received daratumumab at the dose of 16 mg/kg.

In order to test at  $\alpha=0.05$  the null hypothesis that the PFS is less than 3 months versus the alternative hypothesis that PFS is at least 5 months with a power of 90%, 34 patients must be included in the study. This calculation assumes exponential survival curves, an accrual time of 18 months and a length of follow up period of 30 months. Assuming a drop-out rate of about 10%, 38 patients are needed.

Sample size was computed by “SWOG One arm survival sample size and power” ([www.swogstat.org/stat/public/one\\_survival.htm](http://www.swogstat.org/stat/public/one_survival.htm))

## 10.6 Measures to Minimize Bias

### 10.6.1 Enrolment/Masking procedures

#### Patient numbering

Each patient is identified in the study by a Subject Number (Subject No.), that is assigned when the patient is first enrolled for screening and is retained as the primary identifier for the patient throughout his/her entire participation in the trial. The coordinating investigator or designated staff will assign the subject number. Once assigned, the Subject No. must not be reused for any other subject and the Subject No. for that individual must not be changed. If the patient fails to enroll for any reason, the reason will be entered into the Screening Disposition page

#### 10.6.2 Blinding - Unblinding

Since this is an open-label study, the treatment will be open to patients, investigator staff, and personnel performing the assessments.

## 11. Source Documents and Access to source data / documents

Each participating site will maintain appropriate medical and research records for this trial, in compliance with ICH E6 and regulatory and institutional requirements for the protection of confidentiality of participants. Each site will permit authorized representatives of Regulatory Agencies to examine (and when permitted by applicable law, to copy) clinical records for the purposes of quality assurance reviews, audits, and evaluation of the study safety, progress, and data validity.

Source data are all information, original records of clinical findings, observations, or other activities in a clinical trial necessary for the reconstruction and evaluation of the trial. Examples of these original documents and data records include, but are not limited to, hospital records, clinical and office charts, laboratory notes, memoranda, pharmacy dispensing records, recorded data from automated instruments, copies or transcriptions certified after verification as being accurate and complete, microfiches, photographic negatives, microfilm or magnetic media, x-rays, and participant files and records kept at the pharmacy, at the laboratories, and medical-technical departments involved in the clinical trial.

The eCRF will not be the only record of the patient's participation in the study in order to ensure that anyone who accessed the patient's medical record would have adequate knowledge that the patient is participating in the trial.

### **Inclusion/Exclusion Criteria Source Documentation Requirements**

The minimum source documentation requirements for the Inclusion/Exclusion criteria that specify a need for documented medical history (see Section 5.1 and Section 5.2) are the following:

- Referral letter from treating physician
- Complete history of medical notes at the site
- Discharge summaries

## **12. Quality Assurance and Quality Control**

Following written SOPs, the monitors will verify that the clinical trial is conducted and data are generated, documented (recorded), and reported in compliance with the protocol, GCP, and the applicable regulatory requirements [e.g., Good Laboratory Practices (GLP), Good Manufacturing Practices (GMP)].

The investigational site will provide direct access to all trial related sites, source data/documents, and reports for the purpose of monitoring and auditing by the sponsor, and inspection by local and regulatory authorities.

## **13. Ethics/Protection Human of Subjects**

### **13.1 Ethical standards**

This clinical study shall be implemented and reported in accordance with the ICH Guidelines for Good Clinical Practice, all applicable local regulations and with the ethical principles laid down in the Declaration of Helsinki.

### **13.2 Institutional Review Board (IRB)/independent Ethics Committee (IEC) and competent authority**

The protocol, informed consent form(s), recruitment materials, and all participant materials will be submitted to the relevant IRB/EC and Competent Authority (CA) for review and approval. Approval of both the protocol and the consent form must be obtained before any participant is enrolled. Any amendment to the protocol will require review and approval by the IRB/EC and or CA before the changes are implemented to the study. All changes to the consent form will be IRB/EC and/or CA approved; a determination will be made regarding whether previously consented participants need to be re-consented.

